7.2 Reporting of adverse events

Investigators at each site will determine daily if any clinical adverse experiences occur during the period from when the initial ventilator changes are made to 48 hours after initiating unassisted breathing or day 60, whichever occurs first. The investigator will evaluate any changes in laboratory values and physical signs and will determine if the change is clinically important and different from what is expected in the course of treatment of patients with ALI or ARDS. If clinically important and unexpected adverse experiences occur, they will be recorded on the adverse event case report form.

Investigators will report all serious, unexpected, and study-related adverse events, as defined in Appendix B, to the Clinical Coordinating Center within 24 hours. The local Institutional Review Board will also be informed in a timely manner. The investigator will then submit a detailed written report to the Clinical Coordinating Center no later than 5 days after the investigator discovers the event.

The Clinical Coordinating Center will report all serious, unexpected, and study-related adverse events to the FDA or DSMB within 10 working days and will distribute these reports to investigators for submission to their respective Institutional Review Boards. The DSMB will also review all adverse events during scheduled interval analyses. The Clinical Coordinating Center will distribute the written summary of the DSMB's periodic review of adverse events to investigators for submission to their respective Institutional Review Boards in accordance with NIH Guidelines.

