7.3 Site monitoring

Routine site visits will be performed no more than once each year to ensure that all regulatory requirements for the use of investigational agents are being met and to monitor the quality of the data collected. The site visit team will be composed of a research nurse and other members of the Clinical Coordinating Center, a representative of the NHLBI and an investigator from another CCTG. Records of IRB approvals and patient charts will be examined as needed to evaluate the accuracy of the data entered into the database.

8 Risk Assessment

Patients in the Higher ELV/Lower FiO₂ group may experience more hypercapnia. This could cause more dyspnea and agitation, for which they would receive more sedation. Generous sedation (benzodiazepines and narcotics) is given to most critically ill patients because of anxiety and discomfort. There may be additional sedation requirements in the Higher ELV/Lower FiO₂ group. The Higher ELV/Lower FiO₂ study group may also have higher airway pressures, which would indicate higher levels of lung stretch and potential for stretch-induced lung injury. Hypercapnia and respiratory may require more sodium bicarbonate to maintain arterial pH targets. This could cause volume overload or hypernatremia. Fluid balance and serum sodium are assessed frequently in the intensive care units. The potential adverse effects of bicarbonate infusions can be anticipated and avoided, minimized, or counteracted with diuretics and adjustments in fluid management.

Patients in the Lower ELV/Higher FiO₂ group will require higher FiO₂ levels and may be at higher risk of oxygen toxicity. Moreover, they may be at a higher risk of lung injury and inflammatory mediator release from ventilation with atelectasis at end-expiration.

9 Human Subjects

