15. Liver Failure: Child-Pugh Class C, which is defined as a total of 10-15 points on the following scoring table [38].

Points	Class
5-6	A
7-9	B
≥ 10	C

Measurement	Numerical score for increasing abnormality		
	1	2	3
Ascites	None	Present	Tense
Encephalopathy	None	Grade I or II	Grade III or IV
Bilirubin (mg/dl)	< 2	2-3	> 3
Albumin (g/L)	>35	28-35	<28
Prothrombin time (sec. prolonged)	1-4	4-10	> 10

B Adverse Event Reporting Procedure

1. Procedures for Reporting Adverse Events

Assuring patient safety is an essential component of this protocol.

Each participating investigator has primary responsibility for the safety of the individual participants under his or her care.

All adverse events will be evaluated by the Principal Investigator. The Study Coordinator must view patient records for possible adverse events throughout the study period. All adverse events occurring within the study period must be reported in the participants' case report forms.

The investigator will report all serious, unexpected, and study-related adverse events to the Clinical Coordinating Center within 24 hours. The Institutional Review Board must also be informed in a timely manner. The investigator will then submit a detailed written report to the Clinical Coordinating Center no later than 5 days after the investigator discovers the event.

The Clinical Coordinating Center will report serious, unexpected events to the FDA or DSMB in accordance with FDA guidelines.

2. Definitions of Adverse Events

A serious adverse event is any event that is fatal or immediately life threatening, is permanently disabling, severely incapacitating, or requires or prolongs inpatient hospitalization. Important medical events that may not result in death, be life threatening, or require hospitalization may be considered serious adverse experiences when, based upon appropriate medical judgement, they may jeopardize the patient or subject and may require medical or surgical intervention to prevent one of the outcomes listed above.

Life-threatening means that the patient was, in the view of the investigator, at immediate risk of death from the reaction as it occurred. This definition does not include a reaction, which in a more serious form, might have caused death. Assessment of the cause of the event has no bearing on the assessment of the event's severity.

An unexpected adverse event is any experience not identified by type, severity, or frequency in the current study protocol or an

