event that is unexpected in the course of treatment for Acute lung Injury or ARDS.

Adverse events will be considered to be study-related if the event follows a reasonable temporal sequence from a study procedure and could readily have been produced by the study procedure.

Organ failures related to ARDS or a patient's underlying condition should not be reported as adverse events since they are systematically captured by the protocol data collection.

C Schedule of Events

D Procedures for PEEP and FiO₂ adjustments when PEEP/FiO₂ is not compatible with protocol.

- If arterial oxygenation is higher than the target range:
Either FiO₂ or PEEP will be decreased (by .10 or 2, respectively), whichever is farther (number of step changes) from the target scale .
If both PEEP and FiO₂ are equidistant from the scale, then:
 - Lower ELV/Higher FiO₂ Study Group: decrease PEEP first
 - Higher ELV/Lower FiO₂ Study Group: decrease FiO₂ first
- If arterial oxygenation is lower than the target range:
Either FiO₂ or PEEP will be increased (by .10 or 2, respectively), whichever is farther (number of step changes) from the target scale.
If both PEEP and FiO₂ are equidistant from the scale, then:
 - Lower ELV/Higher FiO₂ Study Group: increase FiO₂ first
 - Higher ELV/Lower FiO₂ Study Group: increase PEEP first
- If arterial oxygenation is within the target range:
If a single adjustment in either FiO₂ or PEEP would correct the FiO₂/PEEP to the target scale, then a change in either PEEP or FiO₂ will be made, following the study group priority sequence:
 - Lower ELV/Higher FiO₂ Group: decrease PEEP, increase FiO₂, decrease FiO₂, increase PEEP.
 - Higher ELV/Lower FiO₂ Group: increase PEEP, decrease FiO₂, increase FiO₂, decrease PEEP.

If the FiO₂/PEEP cannot be corrected to the target scale with a single adjustment, then FiO₂ will be adjusted by .10 and PEEP will be simultaneously adjusted in the opposite direction by 2 cmH₂O. E.g.: increase FiO₂ by .10 and decrease PEEP by 2 cmH₂O, or decrease FiO₂ by .10 and increase PEEP by 2 cmH₂O.

E Genetic Testing Information

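### Section 7.2 and Appendix B give different rules for recording adverse events, and three harms foreseen in Section 8 may go unrecorded

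*Supplement*

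**What the plan says.** **Section 7.2, rule and window.** The investigator decides whether a change is "clinically important and different from what is expected in the course of treatment of patients with ALI or ARDS". Then: "If clinically important and unexpected adverse experiences occur, they will be recorded on the adverse event case report form". The period runs from the first protocol ventilator changes to "48 hours after initiating unassisted breathing or day 60, whichever occurs first". The same section says that the DSMB reviews all adverse events at its scheduled analyses.

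**Appendix B, rule.** "All adverse events occurring within the study period must be reported in the participants' case report forms". There is one exemption: "Organ failures related to ARDS or a patient's underlying condition should not be reported as adverse events since they are systematically captured". The study period is not defined.

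**Appendix B, meaning of unexpected.** The definition has two limbs joined by an or. The first is "any experience not identified by type, severity, or frequency in the current study protocol". The second covers an event that is unexpected in the course of treating ALI or ARDS.

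**Section 8.** For the Higher ELV/Lower FiO₂ group it foresees more hypercapnia, with dyspnea, agitation and added sedation, and higher airway pressures. Of the extra bicarbonate that may be needed it says: "This could cause volume overload or hypernatremia". It also names risks for the Lower ELV/Higher FiO₂ group.

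**The concern.** The two sections tell a site coordinator different things about the same task. One filters on importance and expectedness; the other does not filter, apart from organ failures. With about 24 hospitals taking part, adverse event counts could depend on which section a site follows. The DSMB may stop the trial for lack of safety, yet the events put before it would not be a defined set.

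The expectedness filter also sits awkwardly with Section 8. A harm that the protocol itself foresees is one that an investigator can readily call expected. If such a harm is not collected elsewhere on a schedule, the trial may hold no usable record of it for either arm, and the comparison could not be made afterwards.

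**Working it through.** No figure in the plan bears on this point, so there is nothing to reproduce. The check sets the texts side by side.

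**Step 1. The recording rules.**

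| | Section 7.2 | Appendix B |
|---|---|---|
| Which events | Clinically important and unexpected | All |
| Exemption | None stated | Organ failures due to ARDS or the underlying condition |
| Ends | 48 hours after starting unassisted breathing or day 60, whichever is first | End of an undefined study period |

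An expected but clinically important event is reportable under Appendix B and not under 7.2. The amendments, the last dated October 12, 2000, change neither text.

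**Step 2. The window.** Section 4.1.3 has study ventilator procedures resume if positive pressure ventilation is needed again within 28 days of enrollment. Read literally, 7.2 has by then closed recording for a patient who had passed 48 hours after starting unassisted breathing. Appendix B does not say whether its study period covers that time.

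**Step 3. Would a foreseen harm count as expected?** Section 7.2 refers to Appendix B's definitions only in its sentence on 24-hour reporting. The form rule follows 7.2's own yardstick, the usual course of ALI/ARDS treatment. Section 8 says that most critically ill patients are sedated for anxiety and discomfort, so agitation could readily be called expected on that yardstick. On Appendix B's first limb, a harm named in Section 8 is identified by type. Section 8 gives no severity or frequency, however, so a severe or unusually frequent instance could still qualify as unexpected. The second limb leaves further room. On either test exclusion is possible, not automatic.

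**Step 4. What is collected anyway?** Section 8's harms for the Higher ELV/Lower FiO₂ group, set against the on-study list in Section 5.3:

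| Harm | In Section 5.3 |
|---|---|
| Hypercapnia | Yes: arterial PCO₂ and pH |
| Higher airway pressures | Yes: plateau and peak pressure |
| More sedation | Proxy: sedatives, yes/no |
| Volume overload | Proxy: weight |
| Hypernatremia | Not listed; electrolytes appear only at baseline (5.2) |
| Dyspnea | Not listed |
| Agitation | Not listed |

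That is 2 direct + 2 by proxy + 3 not listed = 7. Barotrauma, worst systolic pressure and vasopressor use are also collected. Marked dyspnea is a tolerance criterion in the weaning sections (4.1.2.3 and 4.1.2.5) but not a data item in 5.3. For sodium, Section 8 relies on frequent assessment in the intensive care unit, which is clinical care and not trial data.

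**Step 5. Limit of the check.** The Appendix C table is not shown. Amendment 4 changes the Glasgow Coma Score days through that schedule, so the schedule does set data requirements and might list items that 5.3 does not.

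**The case against.** The strongest reply is that the adverse event form is not this trial's main safety instrument. Section 5.3 says that its data serve to assess safety, and it collects most of the foreseen harms in both arms whatever anyone thinks was expected. Sedative use partly tracks dyspnea and agitation, since Section 8 says they would be treated with sedation. This stands, and it confines the collection gap to three items. A yes/no entry for sedatives is nevertheless a weak stand-in where most patients are sedated.

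A second reply is that 7.2 can be read as supplying the study period that Appendix B leaves open. That is a fair reading and would remove the conflict of windows, but Appendix B does not say so, and the conflict over which events to record would remain. One might also argue that Appendix B means the case report forms in general and 7.2 one particular form; no other place for recording adverse events is described.

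A reader might infer something stronger: that the filter falls mainly on the Higher ELV/Lower FiO₂ group and hides its harms from the DSMB. The documents do not support this. The 7.2 yardstick is the same for both arms, Section 8 also names oxygen toxicity, lung injury and mediator release for the other group, and several of the main foreseen harms are collected on schedule. Nor does it follow that foreseen harms would never be recorded (Step 3).

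**Conclusion.** The conflict between 7.2 and Appendix B is real and stands in the current text. It leaves site recording open to variation, and the DSMB's set of adverse events undefined. The secondary gap is narrower: hypernatremia, dyspnea and agitation may be judged expected under 7.2 and go unrecorded. This assumes that Appendix C does not list them and that some sites follow 7.2 in preference to Appendix B.

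The size cannot be stated in events or patients. The documents give no rate for any of these harms and no indication of how sites would choose between the rules, so counts built on assumed rates would show only the assumptions. The point merits an amendment; it does not touch the primary mortality comparison.

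**What to change.** - State one recording rule and one window in both 7.2 and Appendix B, and keep the existing organ-failure exemption. Define the study period, and say whether recording reopens when study ventilation resumes.
- Say that the adverse events reviewed by the DSMB are the set so defined.
- Add a short check-list, completed in both arms whether or not the event was expected, for the Section 8 harms not otherwise collected: hypernatremia, dyspnea and agitation. Check it first against Appendix C and drop anything already there.
- Use the serious, unexpected and study-related filter only for 24-hour expedited reporting.

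A blanket requirement to record every serious event is not needed. In this population it would take in every death, already the primary endpoint, as well as every prolonged hospital stay, and would override the organ-failure exemption.

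The cost is an amendment to two sections, a small addition to the form, and modest extra recording at sites.

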7.3 Site monitoring

Routine site visits will be performed no more than once each year to ensure that all regulatory requirements for the use of investigational agents are being met and to monitor the quality of the data collected. The site visit team will be composed of a research nurse and other members of the Clinical Coordinating Center, a representative of the NHLBI and an investigator from another CCTG. Records of IRB approvals and patient charts will be examined as needed to evaluate the accuracy of the data entered into the database.

8 Risk Assessment

Patients in the Higher ELV/Lower FiO₂ group may experience more hypercapnia. This could cause more dyspnea and agitation, for which they would receive more sedation. Generous sedation (benzodiazepines and narcotics) is given to most critically ill patients because of anxiety and discomfort. There may be additional sedation requirements in the Higher ELV/Lower FiO₂ group. The Higher ELV/Lower FiO₂ study group may also have higher airway pressures, which would indicate higher levels of lung stretch and potential for stretch-induced lung injury. Hypercapnia and respiratory may require more sodium bicarbonate to maintain arterial pH targets. This could cause volume overload or hypernatremia. Fluid balance and serum sodium are assessed frequently in the intensive care units. The potential adverse effects of bicarbonate infusions can be anticipated and avoided, minimized, or counteracted with diuretics and adjustments in fluid management.

Patients in the Lower ELV/Higher FiO₂ group will require higher FiO₂ levels and may be at higher risk of oxygen toxicity. Moreover, they may be at a higher risk of lung injury and inflammatory mediator release from ventilation with atelectasis at end-expiration.

9 Human Subjects

Each study participant or an appropriate surrogate must sign and date an informed consent form. Institutional review board approval will be required before any subject is entered into the study. All study participants or their surrogates will be informed of the objectives of the study and the potential risks. To maintain confidentiality, all laboratory specimens, evaluation forms, and reports will be identified only by a coded number. All records will be kept in a locked, password protected computer. All computer entry and networking programs will require coded numbers. Clinical information will not be released without the written permission of the patient, except as necessary for monitoring by the FDA, National Heart, Lung, and Blood Institute, and ARDS Clinical Coordinating Center (per 21CFR sec. 50 and 312). Layered informed consent for genetic testing of biological samples will be obtained as outlined in Appendix E.

References

- [9] Pinsky MR. The effects of mechanical ventilation on the cardiovascular system. *Crit Care Clin* 6: 663-678, 1990.

15. Liver Failure: Child-Pugh Class C, which is defined as a total of 10-15 points on the following scoring table [38].

Points	Class
5-6	A
7-9	B
≥ 10	C

Measurement	Numerical score for increasing abnormality		
	1	2	3
Ascites	None	Present	Tense
Encephalopathy	None	Grade I or II	Grade III or IV
Bilirubin (mg/dl)	< 2	2-3	> 3
Albumin (g/L)	>35	28-35	<28
Prothrombin time (sec. prolonged)	1-4	4-10	> 10

B Adverse Event Reporting Procedure

1. Procedures for Reporting Adverse Events

Assuring patient safety is an essential component of this protocol.

Each participating investigator has primary responsibility for the safety of the individual participants under his or her care.

All adverse events will be evaluated by the Principal Investigator. The Study Coordinator must view patient records for possible adverse events throughout the study period. All adverse events occurring within the study period must be reported in the participants' case report forms.

The investigator will report all serious, unexpected, and study-related adverse events to the Clinical Coordinating Center within 24 hours. The Institutional Review Board must also be informed in a timely manner. The investigator will then submit a detailed written report to the Clinical Coordinating Center no later than 5 days after the investigator discovers the event.

The Clinical Coordinating Center will report serious, unexpected events to the FDA or DSMB in accordance with FDA guidelines.

2. Definitions of Adverse Events

A serious adverse event is any event that is fatal or immediately life threatening, is permanently disabling, severely incapacitating, or requires or prolongs inpatient hospitalization. Important medical events that may not result in death, be life threatening, or require hospitalization may be considered serious adverse experiences when, based upon appropriate medical judgement, they may jeopardize the patient or subject and may require medical or surgical intervention to prevent one of the outcomes listed above.

Life-threatening means that the patient was, in the view of the investigator, at immediate risk of death from the reaction as it occurred. This definition does not include a reaction, which in a more serious form, might have caused death. Assessment of the cause of the event has no bearing on the assessment of the event's severity.

An unexpected adverse event is any experience not identified by type, severity, or frequency in the current study protocol or an

event that is unexpected in the course of treatment for Acute lung Injury or ARDS.

Adverse events will be considered to be study-related if the event follows a reasonable temporal sequence from a study procedure and could readily have been produced by the study procedure.

Organ failures related to ARDS or a patient's underlying condition should not be reported as adverse events since they are systematically captured by the protocol data collection.

C Schedule of Events

D Procedures for PEEP and FiO₂ adjustments when PEEP/FiO₂ is not compatible with protocol.

- If arterial oxygenation is higher than the target range:
Either FiO₂ or PEEP will be decreased (by .10 or 2, respectively), whichever is farther (number of step changes) from the target scale .
If both PEEP and FiO₂ are equidistant from the scale, then:
 - Lower ELV/Higher FiO₂ Study Group: decrease PEEP first
 - Higher ELV/Lower FiO₂ Study Group: decrease FiO₂ first
- If arterial oxygenation is lower than the target range:
Either FiO₂ or PEEP will be increased (by .10 or 2, respectively), whichever is farther (number of step changes) from the target scale.
If both PEEP and FiO₂ are equidistant from the scale, then:
 - Lower ELV/Higher FiO₂ Study Group: increase FiO₂ first
 - Higher ELV/Lower FiO₂ Study Group: increase PEEP first
- If arterial oxygenation is within the target range:
If a single adjustment in either FiO₂ or PEEP would correct the FiO₂/PEEP to the target scale, then a change in either PEEP or FiO₂ will be made, following the study group priority sequence:
 - Lower ELV/Higher FiO₂ Group: decrease PEEP, increase FiO₂, decrease FiO₂, increase PEEP.
 - Higher ELV/Lower FiO₂ Group: increase PEEP, decrease FiO₂, increase FiO₂, decrease PEEP.

If the FiO₂/PEEP cannot be corrected to the target scale with a single adjustment, then FiO₂ will be adjusted by .10 and PEEP will be simultaneously adjusted in the opposite direction by 2 cmH₂O. E.g.: increase FiO₂ by .10 and decrease PEEP by 2 cmH₂O, or decrease FiO₂ by .10 and increase PEEP by 2 cmH₂O.

E Genetic Testing Information

Portions of samples collected, processed, and stored as specified in this protocol may be used for genetic analyses in the future. Genetic analysis will involve, in part, the analysis of genomic DNA and will attempt to link genotypic information to the extensive phenotypic information measured as part of this study. A layered informed consent will be used to obtain the study subjects' consent for genetic testing. Consent for the use of these samples for genetic analysis related to the study of ARDS by the ARDS Network Investigators, consent for future studies not necessarily related to ARDS, or consent for genetic testing in both of these categories will be obtained. The level of an individual's consent for testing (e.g. none, for ARDS studies, for future studies, or all studies) will be recorded in the Case Report Forms and stored in the Clinical Coordinating Center Data Base.

Samples are stored at a central repository per ARDS Network protocol. Samples are identified by their ARDSNet Study Numbers. Approved studies for genetic testing will be sent to the CCC where samples that have the necessary level of informed consent for genetic testing will be identified. The CCC will then instruct the repository to prepare the relevant samples for shipment. The samples will have the ARDSNet Study Numbers removed and will be re-labeled with a new number. The Clinical Coordinating Center will be the only site to keep the database, relating the new sample number to the previous ARDSNet Study number, and this will be kept strictly confidential.

Upon completion of Network activities, the CCC will assign new Study Numbers for all ARDSNet Study subjects. The CCC will then instruct the repository to strip all samples of their ARDSNet identifiers and re-label them with the new study subject numbers. This will prevent investigators from using the ARDS Net Study Numbers to identify individual subjects in the future.

Prospective, Randomized, Multi-Center Trial of Higher End-Expiratory Lung Volume/Lower FiO₂ versus Lower End-Expiratory Lung Volume/Higher FiO₂ Ventilation in Acute Lung Injury and Acute Respiratory Distress Syndrome

ALVEOLI

PROTOCOL AMENDMENTS

Changes from the July 20 version of the protocol are in **bold face** type.

Amendment No. 1 Recruitment Maneuver (RM) Procedures

Section 4.1.1.4(c) (page 22 of the July 20, 1999 version of the protocol) is amended as follows:

- (c) **A Recruitment Maneuver (RM) will be performed in the Higher ELV/Lower FiO₂ group between 0600-1000 (reference interval) on days 1 and 3 or on days 2 and 4 after the day of randomization (day 0) if a patient does not meet "Commencement of Weaning" criteria (section 4.1.2). . Odd or even RM days will be assigned by randomization.** Each RM will be documented.

RMs will be performed as follows if systolic pressure = 100-200 mmHg and heart rate = 70-140/min:

- (1) **Initial FiO₂ = pre-RM FiO₂.**
- (2) Ventilation mode will be changed to CPAP = most recent PEEP level.
- (3) CPAP will be increased over ten seconds to **35** cmH₂O (to **40** cmH₂O if measured weight ≥ 150 % PBW).
- (4) CPAP will be maintained at **35** (or **40**) cmH₂O for **30** seconds.
- (5) RM will be terminated immediately and CPAP returned to the most recent PEEP level if any of the following signs of distress occur:
 - Systolic blood pressure decreases to 90 mmHg or by > 30 mmHg.
 - Heart rate increases to > 140/min or by > 20/min.
 - SpO₂ decreases by 5% and is < 88 %.
- (6) After **30** seconds at CPAP = **35** (or **40**) cmH₂O, CPAP will be decreased over five seconds to the pre-RM PEEP level.
- (7) **Most recent ventilator mode and tidal volume will be resumed upon completion or early termination of RM. PEEP and FiO₂ will be adjusted if necessary to maintain arterial oxygenation in the target range.**

- (8) On non-RM days from day 1-4 (e.g. days 2 and 4 in patients assigned to RMs on days 1 and 3), a "Non-RM" time will be assigned between 0600-1000 by the study coordinator. This time will be documented.

Amendment No. 2: Data Collection to assess RM safety and effects on arterial oxygenation and respiratory system compliance.

The following section will be added to the July 20, 1999 version of the protocol:

Section 5.3.2 Recruitment Maneuver Monitoring

The following data will be recorded in all Higher ELV/Lower FiO₂ patients on days 1, 2, 3, and 4 before, during, and after each RM or Sham RM.

1. **PEEP, FiO₂, and SpO₂ at the following times:**
 - a. **Immediately before RM or Sham-RM.**
 - b. **10, 30, and 60 minutes, 2 hours, 4 hours, 6 hours, and 8 hours after each RM or Sham-RM.**
2. **Tidal volume and plateau pressure before and 1, 4, and 8 hours after initiating RM or Sham-RM.**
3. **The highest and lowest SpO₂ in the first ten minutes after initiating RM or Sham-RM.**
4. **Lowest systolic and diastolic blood pressures during the first 10 minutes after initiating RM or Sham-RM.**
5. **Highest and lowest pulse rate during the 10 minutes after initiating RM or Sham-RM.**
6. **Presence of any other dysrhythmia within 10 minutes after initiating RM or Sham-RM.**
7. **Any other adverse event that could be related to a RM during the 24 hours following each RM or Sham-RM.**

After 40 patients have completed the Higher ELV/Lower FiO₂ arm of the trial, RM safety and efficacy data will be reviewed by the ALVEOLI committee, which will offer an opinion regarding continuing or stopping RMs for the remainder of the trial. The DSMB will review the same data and the ALVEOLI committee opinion and will make a recommendation to the ARDS Network regarding continuation of RMs. The decision regarding continuation or stopping will focus primarily on the safety experience. If RMs continue after this review, the frequency of RMs, the RM CPAP level, and the RM duration will be determined by the ALVEOLI committee and DSMB after review of safety and efficacy data.

Amendment No. 3: Endotracheal Suctioning on Pressure Support

The following sentence at the end of section 4.1.1 (page 24 of the July 20, 1999 version of the protocol) will be deleted: “In both study groups, endotracheal suctioning will be conducted after changing the ventilator mode to Pressure Support = 15 cmH₂O.”

Amendment 4: Data Collection - Glasgow Coma Scores

The schedule of events will be modified to require Glasgow Coma Scores on day 0 and the day of hospital discharge. The requirement for GCS on days 4, 7, 14, 21, and 28 will be deleted.

Amendment 5: Exclusion Criteria - Other Trials

The following section will be deleted from the July 20, 1999 version of the protocol:

Section 3.3 Exclusion Criteria, #3

3. Participation in other intervention trials for ALI, ARDS, or sepsis within the past 30 days.

Amendment 6: Exclusion Criteria - Burns

The following section will be deleted from the July 20, 1999 version of the protocol:

Section 3.3 Exclusion Criteria, #10

The following exclusion will be modified:

10. Burns \geq 30% total body surface area

will be changed to:

10. Burns ³ 40% total body surface area.

Amendment 7: Exclusion Criteria Increased ICP

The following section will be modified from the July 20, 1999 version of the protocol.

Section 3.3 Exclusion Criteria, #7 add the word “still”

7. Elevated intracranial pressure (Appendix A), tricyclic antidepressant overdose (if most recent blood level is elevated or no blood level available), Hgb SS, Hgb SC, or conditions in which hypercapnia would **still** be contraindicated (attending physicians will be advised the hypercapnia may occur).

Prospective, Randomized, Multi-Center Trial of Higher
End-Expiratory Lung Volume/Lower FiO₂ versus Lower End-Expiratory
Lung Volume/Higher FiO₂ Ventilation in Acute Lung Injury and
Acute Respiratory Distress Syndrome

ALVEOLI

PROTOCOL AMENDMENT
January 25, 2000

Previous 7 amendments were dated October 7, 1999

AMENDMENT 8 (adopted January 13-14, 2000, ARDS Network Steering
Committee Meeting).

Page 25 of the July 20, 1999 (Version 1) Protocol, item #2, is amended to:

2. Lower EELV/Higher FiO₂ Group: FiO₂ ≤ .40.
Higher EELV/Lower FiO₂ Group: If PEEP ≤ 12 cmH₂O, FiO₂/PEEP will
be changed to .40/8 for ≤ 30 minutes. SpO₂ must remain ≥ 88%
during these 30 minutes. If SpO₂ decreases below 88% during these
30 minutes, the previous FiO₂/PEEP setting will be resumed. No
further efforts to wean will occur this day.

Page 25, the paragraph following item 6 is amended to:

"... If respiratory rate exceeds 35/min during the 5-minute CPAP trial, the
patient will resume A/C ventilation. In Higher EELV/Lower FiO₂ patients,
PEEP/FiO₂ will be returned to the Higher EELV/Lower FiO₂ settings that
existed prior to the change to 8/.40. The patient will be reassessed"

Page 27, section 4.1.2.4 (Subsequent ventilator settings during weaning), item 2
is amended to:

"2. If PS = 10, 15, or 20 cmH₂O is not tolerated, then return to A/C at
PEEP/FiO₂ appropriate to Study Group assignment."

Prospective, Randomized, Multi-Center Trial of
Higher End-Expiratory Lung Volume/Lower FiO₂ versus
Lower End-Expiratory Lung Volume/Higher FiO₂ Ventilation in
Acute Lung Injury and Acute Respiratory Distress Syndrome

ALVEOLI

PROTOCOL AMENDMENT (May 15, 2000)

These amendments were adopted by the ARDS Network Steering Committee on May 15, 2000. The first amendment is designed to achieve greater separation between the study groups in mean PEEP levels. The subsequent amendment is designed to allow both study groups to begin to wean at the same level of oxygenation impairment (FiO₂/PEEP requirement).

I. Page 22 of the July 20, 1999 (Version I) Protocol is amended as follows:

1. In the Higher EELV/Lower FiO₂ study group, the following three FiO₂/PEEP combinations are deleted from the low-end of the FiO₂/PEEP scheme: .30/5, .30/8, .30/10.
2. Clause (b), first sentence: "FiO₂/PEEP setting may not be decreased from its initial level ... in the Higher ELV/Lower FiO₂ group for at least 12 hours after initial protocol ventilator adjustments" is amended to read as follows:
 - (b) FiO₂/PEEP setting may not be decreased below .30/14 in the Higher EELV/Lower FiO₂ group (except for possible weaning as described in the subsequent amendment to section 4.1.2.1.2) during the first 48 hours after initial protocol ventilator adjustments. FiO₂/PEEP setting may not be decreased below .30/12 in the Higher EELV/Lower FiO₂ group (except for possible weaning as described in the subsequent amendment to section 4.4.2.1.2) after 48 hours until 28 days elapse from initiation of protocol ventilator procedures.

II. Page 25, Section 4.1.2.1.2 is amended as follows to allow both study groups to begin to wean if arterial oxygenation can be maintained at or above the target range on FiO₂/PEEP of .40/8. This amendment supercedes a previous amendment dated January 14, 2000:

2. Lower EELV/Higher FiO₂ Group: FiO₂/PEEP ≤ .40/8.

Higher EELV/Lower FiO₂ Group:

- From 12-48 hours after initiation of protocol ventilator procedures: If FiO₂ ≤ .30 and PEEP = 14, FiO₂/PEEP will be changed to .40/8. SpO₂ must remain ≥ 88% for 30 minutes at FiO₂/PEEP = .40/8. If SpO₂ falls below 88%, previous FiO₂/PEEP settings will be resumed. (Recruitment Maneuvers will be conducted as defined in Section 4.1.1 after returning to previous FiO₂/PEEP settings if SpO₂ < 88% during the trial at FiO₂/PEEP = .40/8).
- 48 hours-28 days after initiation of protocol ventilator procedures: If FiO₂ ≤ .30 and PEEP = 12, FiO₂/PEEP will be changed to .40/8. SpO₂ must remain ≥ 88% for 30 minutes at FiO₂/PEEP = .40/8. If SpO₂ falls below 88%, previous FiO₂/PEEP settings will be resumed. (Recruitment Maneuvers will be conducted as defined in Section 4.1.1 after returning to previous FiO₂/PEEP settings if SpO₂ < 88% during the trial at FiO₂/PEEP = .40/8).

The following addition in **bold face type** is a clarification of intent of the July 20, 1999 Version I of the protocol

6. ... If respiratory rate exceeds 35/min during the 5-minute CPAP trial, the patient will resume A/C ventilation at the most recent settings. **(In Higher EELV/Lower FiO₂ patients, recruitment maneuvers will be conducted as defined in Section 4.1.1).** The patient will be reassessed

Prospective, Randomized, Multi-Center Trial of Higher
End-Expiratory Lung Volume/Lower FiO₂ versus Lower End-Expiratory
Lung Volume/Higher FiO₂ Ventilation in Acute Lung Injury and
Acute Respiratory Distress Syndrome

ALVEOLI

PROTOCOL AMENDMENT

October 12, 2000

These amendments remove the recruitment maneuvers from the protocol.

I. On pages 22 and 23 of the July 20, 1999 protocol, delete the following sections: 4.1.1.4c on page 22 and sections a-h on pages 22-23

(2) **Recruitment maneuvers** (RM) will be performed in the Higher ELV/Lower FiO₂ group within one hour of the initial FiO₂/PEEP adjustments, once daily (between 0600-1000), after disconnections of the endotracheal tube from the ventilator circuit, and after coughing or agitation that causes (within 5 minutes) a sustained (≥ 10 minutes) decrease in SpO₂ of $\geq 5\%$ or in PaO₂ of ≥ 15 mmHg. No more than 4 recruitment maneuvers will be performed in any 24-hour interval. Each recruitment maneuver will be documented.

RMs will be performed as follows if systolic blood pressure = 100-200 mmHg, heart rate = 70-140, and there were < 4 RMs in the preceding 24 hours:

- (a) If FiO₂ $< .90$, FiO₂ will be raised to 0.90 for 5 minutes.
- (b) Ventilation mode will be changed to CPAP = most recent PEEP level.
- (c) CPAP will be increased over 10 seconds to 40 cmH₂O (to 45 cmH₂O if measured wt. $\geq 150\%$ PBW).
- (d) CPAP will be maintained at 40 (or 45) cmH₂O for 45 seconds.
- (e) The RM will be terminated immediately and CPAP returned to the most recent PEEP level if any of the following signs of distress occur:
 - Systolic blood pressure decreases to 90 mmHg or by > 30 mmHg.
 - Heart rate increases to > 140 /min or by > 20 /min.
 - SpO₂ decreases by 5% and is $< 90\%$
- (f) After 45 Seconds at CPAP = 40 (or 45) cmH₂O, CPAP will be decreased over 5 seconds to the pre-RM level.
- (g) Most recent ventilation settings (Mode, tidal volume, PEEP/FiO₂, etc) will be resumed upon completion or early termination of RM.
- (h) If 2 RMs require early termination within a single 24 hour interval, no additional RMs will be attempted for at least 12 hours.

II. From the May 15, 2000 ALVEOLI Protocol amendments, delete the following sentences.

On the second page, second paragraph with the heading, "Higher EELV/Lower FiO₂ Group";, delete the following sentence which is included in the second and third paragraphs.

(Recruitment Maneuvers will be conducted as defined in Section 4.1.1 after returning to previous FiO₂/PEEP settings if SpO₂ < 88% during the trial at FiO₂/PEEP = .40/8).

In the paragraph which begins with:

6... If respiratory rate exceeds 35/min during the 5-minute CPAP trial...

delete the following phrase:

(In Higher EELV/Lower FiO₂ patients, recruitment maneuvers will be conducted as defined in Section 4.1.1)

III. Delete amendments 1 and 2 from the October 21, 1999 amendments to the July 20, 1999 protocol

.Amendment #1 is Recruitment Maneuver Procedures; Amendment 2 is Data Collection to assess RM safety
